7.9 Pooling

Subgroup analysis of the primary performance endpoint by center, and US vs OUS, will be used to evaluate the poolability of the results. The significance of center-to-center variability in treatment effect will be evaluated by including an interaction term of treatment group by center in a logistic regression model. In the case that poolability is questionable, the reasons for differential treatment effect, such as patient and clinical characteristics, will be investigated and reported.

8 DATA MANAGEMENT

8.1 Data Capture

Data capture will be performed using an Electronic Data Collection (EDC) system in conjunction with electronic patient reported outcome collection tools implemented in the smartphone application. The clinical sites will use electronic case report forms (eCRFs) to document the information required by the study CIP.

The EDC provider is ClearClinica. The EDC allows for the secure collection, transmission, validation, monitoring and real-time administration of study data gathered at investigative sites, and by the patient via the smartphone application. The system allows password-restricted access to clinical trial information based on individuals' roles and responsibilities. The EDC is compliant with *21 CFR Part 11* and FDA's "*Guidance: Computerized Systems Used in Clinical Trials*."

Except for Patient Reported Outcome entered directly by the patient to the smartphone App, data reported on the eCRF should be driven from source documents and be consistent with these source documents. Editing of data is done under full audit trail.

PRO data collected from the smartphone applications will be saved in dedicated log files on the smartphones for backup purposes and transferred to the EDC system at end of study visit.

8.1.1 Direct Data Entry

For several CRF fields Source Data Verification (SDV) may not be possible as entries may not be found in source documents (e.g., migraine diary or other Patient Reported Outcome completed directly into the smartphone App). Therefore, it is allowed to use the CRF for direct data entry, but only for pre-defined fields.

8.2 Data Quality Assurance

To ensure the quality of clinical data across all subjects, a clinical data management review will be performed by Theranica on patient data submitted in the CRF. During this review, patient data will be checked for consistency, omissions, and any apparent discrepancies. In addition, the data will be reviewed for adherence to the CIP and relevant regulations. To resolve any questions arising from the clinical data management review process, data queries and/or site notifications will be issued by Theranica. Discrepancy resolution will be documented within the database audit trail.

8.3 Electronic Signatures

The PI will electronically sign each individual eCRF after the data has been cleaned, monitored and data reviewed. The electronic signature asserts that the investigator inspected or reviewed the data on the eCRF, the data queries, and the site notifications, and agrees with the content. Any changes made to the data after electronic signature has been applied will result in invalidation of the original signature, and the PI will be required to re-sign the data after reviewing the change(s).

8.4 Verification, validation and securing of electronic data capture system

Verification and validation of the EDC and eCRFs will be performed by a team comprising representatives of the developer, the sponsor and at least one of the participating sites. Verification and validation report will be held by the sponsor.

8.5 Records and Data Retention

Copy of all records (e.g., informed consent documents, source data, safety reports, study device dispensing records, etc.) which support case report forms for this study, will be retained in the files of the responsible investigator for a minimum of five (5) years following notification by the sponsor that all investigations (not merely the investigator's portion) are completed, terminated and/or discontinued. If the principal investigator retires, relocates, or for other reasons withdraws from the responsibility of keeping the study records, custody must be transferred to a person who will accept the responsibility. The sponsor must be notified in writing of the name and address of the new custodian within 5 days after such transfer occurs.

Database will be retained by the EDC system provider for a minimum of 5 years.

8.6 Other Aspects of Clinical Quality Assurance

Site PI or a person designated by the site PI is responsible for establishing and maintaining adherence to the study protocol. Study PI is responsible for addressing quality assurance issues (correcting procedures that are not in compliance with protocol). Study Coordinator is responsible for quality control issues (i.e. correcting errors in data entry).

Theranica will assign a monitor to monitor the investigational sites throughout the study. All outstanding issues and findings that site personnel become aware of will be communicated and handled in agreement with Monitoring Plan.

Sponsor auditing of the site may be done before the completion of the study to ascertain data quality and integrity.

The Food and Drug Administration (FDA) and/or the local state health authorities may request access to all study records, including source documents, for inspection. The investigator and site staff agree to cooperate with these audits. The investigator must notify the sponsor of any health authority audit as soon as notification of such audit is made. A representative or designee of sponsor may be present during health authority audit.

9 AMENDMENTS TO THE CLINICAL INVESTIGATION PLAN

The protocol is not to be amended by the investigator without first obtaining sponsor's approval. Amendments initiated by the sponsor, or initiated by the investigator and then approved by the sponsor, will be submitted for approval to local IRB/EC and, if applicable, to the respective Regulatory Authority (RA). Protocol amendments should receive the IRB/EC approval, and if submitted to the RA, a regulatory approval as well, prior to implementation in the study. For non-substantial changes (e.g. minor logistical or administrative changes, change of monitor(s), telephone numbers, renewal of insurance) not affecting the rights, safety and well-being of human subjects or not related to the clinical investigation objectives or endpoints, a simple notification to the IRB/ EC and, where appropriate, regulatory authorities can be sufficient.

The following documents are relevant to the protocol, but are not considered part of the protocol. They are stored and modified separately. As such, modifications to these documents do not require protocol amendments.

- Site Roster
- Case report forms
- Data Management Plan
- Monitoring Plan
- Statistical Analysis Plan
- DMC

10 CLINICAL INVESTIGATION PLAN DEVIATIONS

A protocol deviation is any noncompliance with the clinical study protocol, Good Clinical Practice, or related SOPs requirements. The noncompliance may be on the part of the subject, the investigator, or study staff.

The protocol is not to be deviated by the investigator or the co-investigators without first obtaining sponsor approval except in cases where the safety and well-being of a patient will be affected, as stated in section 4.5.4 b of the ISO 14155 (2011).

Compliance to the protocol will be assessed by study monitor during monitoring visits as well as remotely, using designated reports provided by the EDC system.

All deviations from the protocol will be addressed in study subject source documents and promptly reported to the site IRB, according to local requirements.

10.1 Procedures for Recording, Reporting and Analyzing Protocol Deviations

All protocol deviations need to be documented in source documents and appropriate eCRF.

The Study Monitor is responsible for identifying and reviewing protocol deviations with the investigator or designee and documenting the issue and action/outcome of the protocol deviation in the MVR and any follow up letter / communication to the principal investigator.

The Study Monitor will ensure that major protocol deviations are discussed with the Investigator. Major deviations are those deviations that:

- impact patient safety
- alter the risk/benefit ratio
- compromise the integrity of the study data
- affect willingness of the patient's participation in the study

Deviations will be reported to the IRB/EC periodically or as specified by local regulations. Further documentation of any changes in research activity should be submitted to the sponsor and the IRB/EC if:

- They are related to any instance of serious or continuing non-compliance with governing regulations/requirements of the IRB/EC, and/or
- Related to changes in protocol specified patient activity and procedures.

The Study Monitor will, in addition to the above immediate reporting, document all deviations in the monitoring visit report and follow-up letters. The monitor will discuss deviations with relevant site personnel. If needed, a Note to File will be issued and filed in the relevant file and a copy sent to Theranica.

Theranica or its designee will review records of deviations and will consider the need for corrective and preventive action and further external reporting to regulatory authorities. Deviations will be summarized and included in the study report. Assessment and discussion of their potential impact / lack of impact on study results will be addressed.

10.2 Notification Requirement and Timelines

Major deviations should be escalated to the sponsor within 5 business days.

11 PROTOCOL DEVIATIONS

Protocol deviations must be reported to local IRB/EC per their guidelines. The site PI or other designated site staff member is responsible for knowing and adhering to local IRB/EC requirements. Device Accountability

Devices will be provided by Theranica Bioelectronics, bearing required labeling. Upon being handed to study participant, device number will be documented in CRF and in site log. Each batch of devices delivered to clinical sites for allocation to study participants is accompanied by a shipment note. Device shipment records are maintained by sponsor and on site.

Prior to distribution, the devices are stored in a designated locked cabinet. Access to investigational devices is controlled by the research staff. The devices are only used in the clinical investigation and according to the study protocol.

Each device has a sticker on it with a unique number. When a device is handed to a study participant, it is coupled to the participant's smartphone by means of Bluetooth connection.

In the course of device allocation, application installation and device – application connection establishment, site allocated User ID is entered by study coordinator via the Application.

The triplet of IDs (User ID, phone ID, device ID) provides means of identifying technical and PRO data from each participant in the electronic database while protecting participant's privacy.

The clinical investigator will be responsible for the safe storage of devices in accordance with instructions given by Theranica Bioelectronics, with restricted access to the investigational materials in their possession, thereby preventing use of any materials by any person not participating in the study. Device accountability records will be reviewed during monitoring visits.

The investigator will be responsible for providing device use training to the patients according to the IFU and protocol and for maintaining product inventory and records.

As part of study closure, all unused devices must be returned in their original packaging to Theranica Bioelectronics.

12 STATEMENTS OF COMPLIANCE

This study will be conducted in compliance with the protocol (after being approved by the local EC and, if required, by the local RA), the Good Clinical Practice (GCP) per ISO 14155 (2011) standard and the ethical principles that have their origin in the Declaration of Helsinki.

The Informed Consent Form (ICF), patient's information material, and advertising material (if applicable) must be submitted and approved by the IRB/EC (and RA when needed), and any request by the IRB/EC or RA will be followed. Written approval of the protocol, ICF, patient's information material, and any advertising material (if applicable) must be obtained from the EC and if applicable the corresponding RA prior to any patient enrollment.

Adequate insurance policy will be held valid for the entire study duration as well as for the discovery period required per local regulation.

13 INFORMED CONSENT PROCESS

Written informed consent must be obtained from each study patient prior to commencing any CIP-specific procedures. A written informed consent (approved by Theranica and the IRB/EC) must be signed and dated by the patient, and the person who conducted the informed consent discussion. Additionally, the person who conducted the informed consent discussion will indicate that Informed Consent has been obtained by noting so in the appropriate section of the. Patients will be given a copy of the signed informed consent document. The signed informed consent will be retained with the study records at the investigational site. New findings relevant to the patient's continued participation will be made available to the patients after approval of such updates by the IRB/EC.

Informed consent accurately describes all aspects of the clinical investigation that are relevant to the subject's decision to participate in the study.

14 ADVERSE EVENTS

Capturing of adverse events will serve for safety evaluation.

Adverse events encountered during treatment will be captured via end of study questionnaire and interview.

This study will use the list in section 14.7 below for nomenclature of adverse events complications reported in the CRF for Device related side effects.

Non-Device adverse events will be graded according to section 14.2.1 below. AE resulting from a procedure that is not related to the device, are considered as general AEs.

On-site visits to investigate adverse events and follow them up will be scheduled at the discretion of the principal investigator. Unscheduled visits and termination visit will be reported using designated case report forms.

If at the last visit there will be a Device related AE/side effect that is still active, the patient will be followed to completion or until a steady state is achieved for a continuous period of 2 weeks.

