6.5.9 Patient lost to follow-up

If a patient does not show for a end-of-study visit and cannot be contacted to collect follow-up information, he/she will be counted as a 'missed visit'. Prior to counting the patient as a 'missed visit' the following will be performed:

- Repeated, documented attempts to contact the patient via all available means.
- Repeated, documented attempts to contact the patient's general practitioner or referring physician.
- If a visit cannot be arranged, obtain as much information as possible through all communication means with the patient and/or his/her treating physician.

If a patient is lost to follow-up, the methods used to attempt to contact the patient should be noted. At least three attempts should be made to contact the patient and/or his/her treating physician via all available routes, and a certified letter should be sent to the permanent address on file.

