7.4 Sample Size Estimation

The sample size for this study was calculated to test the above described null hypothesis with a chi-squared test, even though the final analysis may employ a regression model.

In the pilot study, the percentage of responders in the relevant treatment arm was 30%, while the percentage of responders in the sham group was 6%. The latter result is consistent with sham response rates referenced in IHS Guidelines for Migraine Trials. Sample size calculations are based on a more conservative estimate of the sham group response rate of 10%, then a sample size to detect a difference between treated and sham groups (of 20%) with 80% power at a 5% level of significance will result in a total of 124 evaluable subjects, with 62 subjects randomized to the treated arm and 62 to the sham arm. Allowing for a ~10% drop-out rate, a total of 136 (68 treated vs. 68 sham) subjects may be enrolled in the study.

Statistical considerations require availability of 124 evaluable subjects, i.e. with data available for analyses. The study recruitment will be monitored closely via the EDC system and, as soon as the evaluable data target is achieved, the Study Monitor will receive notification. If the number of subjects enrolled in the US is at least 50% of the accumulated population, recruitment will be stopped.

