7.7 Analysis sets

7.7.1 *Intent to treat analysis set (ITT)*

The ITT analysis set will consist of all subjects randomized. In accordance with the ITT principle, all subjects randomized will be kept in their originally assigned treatment group.

7.7.2 *Modified intent to treat analysis set (mITT)*

The mITT set will consist of all subjects in the ITT set who completed at least one study treatment, assigned a treatment group as treated.

7.7.3 *Per protocol analysis set (PP)*

The Per-Protocol (PP) analysis set includes all patients from the mITT analysis set without any major protocol deviation who have evaluable data on at least one qualifying migraine attack.

7.7.4 *Statistical analysis of analysis sets*

The ITT analysis set will serve as the main set for safety assessments and the mITT set for all performance assessments.

The primary performance assessment will also be performed on the PP analysis set as a sensitivity analysis.

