Patient global impression of change will be summarized by descriptive statistics per treatment group and compared between the groups with a t-test.

Ease of use will be summarized by descriptive statistics.

7.8.6 *Safety Analysis:*

The primary safety variable, the cumulative incidence (and 95% CI) of device related adverse events (AEs) throughout the study, will be presented in tabular format and will include incidence tables by severity.

Adverse event rates will be compared between the study groups with a chi-squared test.

Serious adverse events will be listed and discussed individually.

Treatment tolerability will be compared between the study groups, the number and percent of subjects who fail to complete the study and the number and percent of subjects who fail to complete the study because of Adverse Events will be presented as well.

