14.6 Adverse Event Reporting Forms

The eCRFs for AE or SAE will include all relevant information of the AE or SAE with regards to onset and resolution time, grade, causality to device, treatment given etc.

14.7 Foreseeable Complications and Anticipated Adverse Device Related Effects.

Possible adverse events associated with Transcutaneous Electrical Nerve Stimulation include, but are not limited to the following:

- Likely
 - Minor skin irritation from wearing the device, which disappears shortly after the treatment is over.
- Less Likely
 - Red marks at the site of stimulation, that disappear shortly after the treatment is over.
 - Possible sensation of slight warmth where the device touches the skin. This disappears shortly after the treatment is over.
 - A sensation of itching or tingling or stinging at the site of stimulation, which disappears shortly after the treatment is over.
 - Slight muscle fatigue or weakness in arm where the device is applied, which disappears shortly after the treatment is over.
- Very unlikely
 - Slight muscle spasms in the arm where the device is applied, which disappears shortly after the treatment is over.

The following migraine symptoms are foreseeable and will not be considered as device related: headache, nausea, light sensitivity, sensitivity to noise or odors, stomach upset, abdominal pain, loss of appetite, cold or heat sensation, paleness, fatigue, dizziness, fever (rare), blurred vision, bright flashing dots or lights, blind spots, wavy or jagged lines (aura).

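### Routine adverse-event capture rests on end-of-study recall, and the plan does not say how randomised subjects without an adverse-event assessment enter the primary safety incidence

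*Combined protocol and SAP*

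**What the plan says.** Device-related adverse effects are the primary safety endpoint (Synopsis). Section 7.8.6 defines the analysis: "The primary safety variable, the cumulative incidence (and 95% CI) of device related adverse events (AEs) throughout the study" is tabulated by severity, and "Adverse event rates will be compared between the study groups with a chi-squared test". The population is set in 7.7.4: "The ITT analysis set will serve as the main set for safety assessments and the mITT set for all performance assessments". Under 7.7.1, "The ITT analysis set will consist of all subjects randomized", so it includes subjects who never treated an attack.

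On collection, section 14 says: "Adverse events encountered during treatment will be captured via end of study questionnaire and interview". Section 6.6.2 places the end-of-study visit three months after enrolment and has subjects asked then about events over the whole study. Section 14.7 describes the expected device effects as transient, several of them in the words "which disappears shortly after the treatment is over".

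For a subject who does not attend the final visit, 6.5.9 requires repeated contact attempts and as much information as can be obtained by other means. Section 7.8.7 gives missing-data methods for the primary response and allows them for secondary and exploratory endpoints. It does not mention safety.

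**The concern.** Three features combine.

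- **Timing.** The effects expected from this device fade soon after a session, but the stated point of capture is the end of the study. A mild effect in the first treated attack has to be remembered across the rest of the treatment stage.
- **Prompting.** The end-of-study questionnaire in Appendix B asks about itching, redness and heat. Section 14.7 also lists tingling or stinging, muscle fatigue or weakness, and muscle spasm. These would have to be volunteered at interview.
- **Counting.** With all randomised subjects in the safety set and no rule for a missing assessment, a table programmer would probably leave unassessed subjects in the denominator with no event. Nothing requires the number assessed to be shown.

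Forgotten events, and unassessed subjects left in the denominator without an event, both lower the reported incidence. If either differs between arms, the chi-squared comparison is affected as well. The Data Monitoring Committee is to review adverse events during the study (6.4.6), but data collected by the stated route arrive only as subjects finish.

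**Working it through.** **1. Is there any other scheduled query of every subject?**

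| Source | What it provides | Structured adverse-event question to all before study end? |
|---|---|---|
| App screens at start, 2 h and 48 h (6.4.2) | Pain and (start and 2 h) symptoms; medication and optional free text at 2 h and 48 h | No |
| Follow-up calls (6.6.1) | Medical condition, concomitant medication, migraine therapy | No; adverse events not named |
| Pilot study calls (4.2) | The same items plus adverse effects | Named there, absent here |
| Early discontinuation visit (Synopsis, 6.6.1) | Withdrawals only | No |
| Unscheduled visits (section 14) | At the investigator's discretion | No |
| Expedited reporting (14.5) | Clocks start when staff learn of an event or decide to withdraw a subject | No; they act on known events |
| Synopsis and 6.1 | State that adverse events are reported, without a method | No |

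**2. Recall interval.** Roll-in lasts one month and the final visit is at three months. The maximum gap is 3 − 1 = 2 months, about 8 weeks. It is shorter for later attacks, and shorter if the termination visit follows the fourth treated attack, as 6.6.1 suggests.

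**3. The plan's own figures (7.4).** With 30% versus 10%, two-sided 5%, 80% power and pooled variance without continuity correction:

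n per arm = [1.96·√(2·0.2·0.8) + 0.842·√(0.3·0.7 + 0.1·0.9)]² / 0.2² = 61.6, rounded up to 62, total 124.

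This reproduces the stated 124. The plan then adds drop-out, "Allowing for a ~10% drop-out rate", to reach 136. By formula this is 137 (124 × 1.10, rounded up) or 138 (124 / 0.90), close to the stated figure. These are performance figures; the plan states no safety rate or precision. They are used here only for the allowance: 136 − 124 = 12, and 12/136 = 8.8%.

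**4. Effect of unassessed subjects.** Let p be the incidence (assumed; the documents give none) and m the unassessed share, with missingness unrelated to events.

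- Counted as event-free: p(1 − m)
- Counted as events: p(1 − m) + m

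With p = 10%:

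| m | Event-free | All events |
|---|---|---|
| 5% (assumed) | 9.5% | 14.5% |
| 8.8% (12/136) | 9.1% | 17.9% |
| 10% (assumed) | 9.0% | 19.0% |
| 20% (assumed) | 8.0% | 28.0% |

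Under event-free scoring the relative understatement equals m whatever p is.

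**5. Scale against sampling error.** In one arm, 6 events give 6/68 = 8.8% (exact 95% CI 3.3 to 18.2) on all randomised, and 6/62 = 9.7% (3.6 to 19.9) on those assessed.

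**6. Unequal loss (assumed).** With 20% of sham and 5% of active subjects unassessed, an equal 10% would appear as 8.0% versus 9.5%.

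**The case against.** The plan is not silent outside the final visit. The missed-visit case has a procedure (6.5.9), withdrawals have their own visit, and 14.5 requires device-related side effects to be reported and recorded in monitoring-visit or call summaries. A call that asks about changes in medical condition could bring out an adverse event. The eCRF structure sits in a Data Management Plan that is not among the documents. All of this stands. A reader might infer that a subject who misses the final visit cannot be scored for safety; the documents do not support that. Nor do they say that such a subject is counted as event-free. That is a likely default under ITT with no rule given.

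The arithmetic is also modest. A shift from 10% to 9.1% lies well inside the interval for one arm. The drop-out allowance concerns evaluable performance data and may include subjects who never treated, for whom no treatment-time device effect is possible, or withdrawals who were seen. It is a convenient ceiling, not an estimate of missing safety data.

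A reader might also take the pilot's complete-reporting figures (70% for the three stronger programs, 28% for placebo) as evidence that adverse events will be under-reported unequally by arm. Those figures are completeness of treatment feedback per activation, in a cross-over where each unit carried active and placebo programs. They do not measure visit attendance or adverse-event recall.

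What the objection does not remove is that no scheduled, structured query reaches every subject before study end, that the questionnaire covers only part of the 14.7 list, and that the analysis has no rule for unassessed subjects.

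**Conclusion.** The point holds as a gap in ascertainment and in analysis rules. As written, the primary safety incidence rests largely on recall up to about eight weeks old, partly unprompted, with no stated treatment of ITT subjects who have no assessment.

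The quantifiable part is small on one side and wide on the other: 9.1% to 17.9% around an assumed 10%, if the whole drop-out allowance were unassessed. This rests on the assumed 10% incidence among assessed subjects and on using 12 of 136 as the unassessed share. Forgetting would lower the figure further, but the documents give no basis for a rate, and a specific recall-loss scenario would be assumption throughout. The case for change therefore rests on how the data are collected and on the missing rule, more than on the one-point shift.

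**What to change.** 1. **Sections 6.6.1 and 14.** Add a non-leading adverse-event question to each scheduled follow-up call. Reconcile the capture sentence in section 14 with 14.5 and with the statements in the Synopsis and 6.1 that adverse events are reported.
2. **Appendix B.** Extend the end-of-study items to every effect listed in 14.7.
3. **Section 7.8.6.** Report per arm the number of treated subjects with at least one adverse-event assessment by any route (call, early discontinuation, unscheduled or final visit). Give the incidence on that denominator beside ITT, and show unassessed treated subjects both as event-free and as events. Subjects assessed only at the final interview must stay in.

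An app item is optional, and only with neutral, open wording. Section 6.2.2 says subjects will not be asked directly about treatment perception, while 6.1 and 6.4.1 collect it; those statements should be reconciled first. Showing the 14.7 list after each attack could cue expectations.

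Cost: a slightly longer call, a few questionnaire items and two or three table rows. Expect somewhat more mild events reported, and a little more staff exposure to subjects' descriptions of sensation, which matters for blinding and argues for a short, scripted question.
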